2 OBJECTIVES

2.1 Safety/Efficacy

2.1.1 Primary Objective

A. Determine if objectively lower rates of significant radiation dermatitis occur with Dermaprazole for HNC patients receiving radiation when compared to patients receiving Aquaphor. An objective measure will be tabulated: the rate of clinically significant (CTCAE version 5 grade 2 or higher) radiation dermatitis. This measure will be reported weekly during treatment by both the treating radiation oncologist and blinded review by a board-certified dermatologist via medical photography.

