2.1.2 Secondary Objectives

2.2.2.1

To assess the highest grade of CTCAE version 5 radiation dermatitis during radiation treatment

2.2.2.2

To assess the time to occurrence of CTCAE version 5 grade 2 or higher acute radiation dermatitis.

2.2.2.3

To assess the time to healing if CTCAE version 5 grade 2 or higher acute radiation dermatitis develops.

2.2.2.4

To evaluate quality of life via acute and long-term symptoms and symptom scores utilizing the SkinDex16 scoring system.

2.2.2.5

To evaluate the threshold dose at which RD appears in either arm, utilizing skin dose tracking structures (V20 to V80 in 5 Gy increments reaching skin shell contours of "skin minus 3 millimeters" and "skin minus 5 millimeters")

2.2.2.6

To evaluate the threshold dose at which RD appears in either arm, using the same metrics as in 2.2.2.5, but with a new simulation scan in the last week of radiotherapy

2.2.2.7

To evaluate the effect of dermaprazole on inflammatory markers: CRP, TNFa, IL-1b, IL-6, by measuring values before, during, and after treatment. We expect this to give further evidence for the mechanism of action of dermaprazole.

Page 4 of 23

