5.5 Assessments & Labs During Treatment

Weekly on-treatment assessments are as follows:

- Focused skin exam
- Adverse event/toxicity evaluation, including CTCAE version 5 evaluation of radiation dermatitis with note of components (erythema, epilation, fibrosis, etc)
- SkinDex16 questionnaire
- Photographic documentation of skin reaction with dermatologist's evaluation of CTCAE version 5 from this photography (photography may be discontinued if dermatitis radiation has resolved, or does not occur, at the discretion of the treating investigator or Principal Investigator)
- Compliance diary
- WBC, Hgb, ALT, AST, creatinine and calcium taken from standard care clinical labs
- Research Blood Draw to Central Lab: CRP, TNFa, IL-1b, IL-6 (in the last week of radiation and at 2 weeks after end of radiation)

Page 10 of 23

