5.6 Post-Treament Follow-Up

Patients will be followed for up to 60 months after completion of radiation or until death to assess intervention-related tolerance. See study calendar.

- 1. Month 1 visit (30 days after completion of all radiation therapy, +/- 14 days)
- 2. Month 3 visit (90 days after completion of all radiation therapy, +/- 28 days)
- 3. Long Term Follow-Up Visits: Month 6 (M6), Month 9 (M9), Month 12 (M12), Month 18 (M18), Month 24 (M24), Month 36 (M36), Month 48 (M48), and Month 60 (M60) (calculated from completion of all radiation therapy, +/- 28 days)

Assessments include:

- Focused skin exam
- Adverse event/toxicity evaluation, including CTCAE version 5 evaluation of radiation dermatitis with note of components (erythema, epilation, fibrosis, etc)
- SkinDex16 guestionnaire
- Photographic documentation of skin reaction with dermatologist's evaluation of CTCAE version 5 from this photography

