6 TREATMENT EVALUATION

6.1 Calendar of Study Assessments & Testing

		Head/Neck RT(Weekly) ^a								
	Baseline	Week 1	Week 2	Week 3	Week 4	Week 5	Week 6	Week 7	Week 8	Week 9 ^h
SCREENING										
Written Informed Consent	Х									
Inclusion/Exclusion Criteria	Х									
PHYSICAL										
Comprehensive History and Physical (ECOG only at Baseline)	Х									
Focused Skin Exam (Radiation Oncologist)	Х	Х	Х	Х	Х	Х	Х	Х		
Medical Photography ^d	Χ	X	Х	Х	Х	Х	Х	Х		
ASSESSMENTS										
CTCAE Version 5 Radiation Dermatitis (Radiation Oncologist)		Х	Х	Х	Х	Х	Х	Х		
CTCAE Version 5 Radiation Dermatitis (Blinded – Dermatologist)		Х	Х	Х	Х	Х	Х	Х		
Adverse Events/Toxicity		Х	Х	Х	Х	Х	Х	Х		
SkinDex16 Questionnaire	Χ	Х	Х	Х	Х	Х	Х	Х		
TREATMENT										
CT Simulation	Х							Χg		
XRT		Х	Х	Х	Х	Х	Х	Х		
Dermaprazole or Aquaphor ^c	Х	Х	Х	Х	Х	Х	Х	Х	Х	Х
Compliance Assessment	X ^f	X	Х	Х	Х	Х	Х	Х		Х
LAB DRAW										
Serum Pregnancy Test if Woman of Child-Bearing Potential	Х									
WBC, Hgb, ALT, AST, creatinine, calcium captured from clinical labse	Х	Х	Х	Х	Х	Х	Х	Х	Х	Х
Research Blood Draw to Central Lab: CRP, TNFa, IL-1b, IL-6	X							Xp		Х

- (a) Weekly assessments to be performed within +/- 3 days of the end of each week (defined by a period of 5 treatments).
- (b) In the last week of radiotherapy, may be different than week 7 $\,$
- (c) See Section 5.3 for detailed instructions regarding Dermaprazole and Aquaphor
- (d) Photos will be taken with a Canon EOS Rebel T7 DSLR Camera with 18-55mm Lens. Photos will be uploaded to a protected research folder directly from the camera and the dermatologist will have access to the folder. The photos will be de-identified and labeled with study case number.
- (e) WBC, Hgb, ALT, AST, creatinine and calcium data will be obtained from standard care clinical labs during treatment. If labs are not being drawn then they will not be obtained for the study.
- (f) Compliance assessment may be performed by telephone by research staff from Baseline to start of XRT
- (g) CT Simulation to be done anytime during the last 7 days of radiation treatment
- (h) Week 9 is defined as 2 weeks post last radiation treatment ± 5 day

Page 12 of 23

	Post-Treatment Assessment		Long Term Follow-Up Up to 60 months post-tx		
	Month 1 30 days post-tx ⁱ	Month 3 90 days post- ^{txj}	Every 3 Months M6, M9, M12j	Every year M24, M36, M48, ^{M60j}	
PHYSICAL					
Focused Skin Exam (Radiation Oncologist)	X	X	X	X	
Medical Photography	X	X	X	X	
ASSESSMENTS					

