8.3 Analysis of Primary and Secondary Endpoints

Descriptive and summary statistics will be computed for demographic and clinical data of all subjects enrolled in the study to describe the study sample.

Toxicity will be reported as the frequency of each adverse event according to the CTCAE version 5.0 as well as the grade of each recorded adverse event (38). Generally, adverse events in this system are graded from 1 to 5, with 1 corresponding to either mild or asymptomatic clinical manifestations of toxicity and 5 corresponding to death related to the

Page 15 of 23

adverse event (see Appendix 2). Clinically relevant toxicity will be defined as grade 2 or higher, while severe toxicity will be defined as grade 3 or higher. Acute toxicity will be defined as adverse events that occur during or within 90 days after completing radiation therapy. We will consider this intervention safe if there is a grade 1 toxicity rate of <50%, a grade 2 or higher toxicity rate of <10% and no grade 3 or higher events.

Percentages of patients enrolled per month will be recorded. If the enrollment time exceeds 24 months, the study will be considered not feasible as written. Percentage of patients not enrolled will be summarized by cause.

Quality of life will be measured with the use of SkinDex16 questionnaires filled out by the patient at baseline, throughout treatment, at the completion of radiation treatment, and at each follow up visit subsequently. We will also consider the compliance to questionnaire completion and within questionnaires completion rates. This will be reported as the average proportion of questions within each form completed properly, without errors. As long as the rates are not below the minimum threshold defined above, the study will be considered feasible.

All analyses outside of the primary endpoint will be considered exploratory in nature. Chi square and t-test will be used to evaluate differences in categorical and numerical values between arms. Subgroup analyses for BMI, total dose, and comorbidity will be conducted. We will also evaluate the incidence of RD for specific radiation skin dose stratification by reviewing the V20 to V80 in 5 Gy increments reaching a skin shell representing the thickness between the skin and the "skin minus 3 millimeters" and the "skin minus 5 millimeters." This will be done on both the original dosimetry as well as a recalculated plan from the resimulation scan.

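### Time to grade 2+ dermatitis and time to healing are secondary objectives, but section 8.3 names only chi-square and t-test and gives no rule for patients without an event

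*Combined protocol and SAP*

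**What the plan says.** Section 2.1.2 sets two time-to-event objectives: "To assess the time to occurrence of CTCAE version 5 grade 2 or higher acute radiation dermatitis" and "To assess the time to healing if CTCAE version 5 grade 2 or higher acute radiation dermatitis develops". Section 8.3, which covers both primary and secondary endpoints, gives one sentence on between-arm testing: "Chi square and t-test will be used to evaluate differences in categorical and numerical values between arms". It labels everything outside the primary endpoint exploratory and makes all tests two-sided. Section 8.4 says who is analysed: patients with at least 60 Gy who are followed up 30 days after treatment.

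The document names no time origin, censoring rule or time-to-event method. It does not define healing. It does not say whose grade dates an event, although there are two graders: "This measure will be reported weekly during treatment by both the treating radiation oncologist and blinded review by a board-certified dermatologist via medical photography". Section 5.5 adds that "photography may be discontinued if dermatitis radiation has resolved, or does not occur, at the discretion of the treating investigator or Principal Investigator".

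On timing, note (a) of section 6.1 reads "Weekly assessments to be performed within +/- 3 days of the end of each week". The calendar shows skin grading through week 7 and none at weeks 8 and 9. Section 5.6 then schedules the "Month 1 visit (30 days after completion of all radiation therapy, +/- 14 days") and the "Month 3 visit (90 days after completion of all radiation therapy, +/- 28 days"). Sections 8.3 and 10.3 define acute toxicity as occurring during treatment or within 90 days of its completion.

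**The concern.** A patient who never reaches grade 2 has no onset time, and a patient whose skin has not recovered has no healing time. A t-test cannot use a censored time as such, so the analyst must either leave these patients out or give them a substitute date. The plan does not say which.

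Leaving them out compares subsets formed after randomisation by the primary outcome itself. Substituting a date makes the reported delay depend on the date chosen, and that choice could be made after the data are seen. At stake are the usefulness and reproducibility of two listed secondary results, not the trial's main conclusion.

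**Working it through.** **Inputs.** From section 8.2: 30 and 15 evaluable patients, grade 2+ rates of 20% (Dermaprazole) and 65% (Aquaphor), alpha 0.05, power 80%, 2:1 allocation. From section 8.3: two-sided tests. The shape of the onset curve is not in the document and is assumed below.

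**Step 1: reproduce the plan's sample size.** Two proportions, pooled variance under the null, no continuity correction. The pooled rate is (0.65 + 2 × 0.20)/3 = 0.35.

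Control n = [1.96 √(0.35 × 0.65 × 1.5) + 0.8416 √(0.65 × 0.35 + 0.20 × 0.80/2)]² / 0.45² = (1.145 + 0.467)² / 0.2025 = 12.8, rounded up to 13. The total is 13 + 26 = 39, as stated. The sample size is not in question.

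**Step 2: patients with no onset time.**
- Dermaprazole: 30 × 0.20 = 6 events, 24 event-free.
- Aquaphor: 15 × 0.65 = 9.75 events, 5.25 event-free.
- Total: 15.75 events; 29.25 of 45 patients (65%) event-free.

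**Step 3: what log-rank could do.** Under assumed proportional hazards the two rates imply HR = ln(0.80)/ln(0.35) = 0.223/1.050 = 0.21. Schoenfeld power with 15.75 events and 1/3 v 2/3 allocation is Φ(√(15.75 × 2/9) × |ln 0.2126| − 1.96) = Φ(1.871 × 1.549 − 1.96) = Φ(0.94), or about 83%. About 15 events are needed for 80% power.

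**Step 4: simulated comparison at 20% v 65%.** 30 v 15 patients, proportional hazards, weekly grading over 7 weeks, Weibull shapes 1, 2 and 4, 3,000 trials per shape, two-sided 0.05.

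| Analysis | Rejection, shapes 1 / 2 / 4 | Mean delay (weeks) |
|---|---|---|
| t-test, affected patients only | 0.081 / 0.070 / 0.059 | 0.47 / 0.39 / 0.24 |
| t-test, event-free set to week 7 | 0.777 / 0.712 / 0.615 | 1.71 / 1.13 / 0.62 |
| Log-rank, all 45 | 0.876 / 0.872 / 0.878 | – |
| Chi-square on incidence (uncorrected) | 0.861 / 0.853 / 0.865 | – |

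A separate run of 10,000 trials with constant hazards gave 7.4% for affected patients only and 87.7% for log-rank. With equal rates of 65% in both arms, all methods reject in about 4–6% of trials, so the differences above are not caused by inflated error. Setting event-free patients to week 7 amounts to a restricted mean when everyone is followed that long. It is a valid test, but less sensitive here than log-rank.

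**Step 5: healing dates.** Month 1 falls on days 16–44 after radiation (30 ± 14) and Month 3 on days 62–118 (90 ± 28). The last weekly grading is within 3 days of the end of week 7. Taking that as the end of radiation, the scheduled gaps are 16 − 3 = 13 to 44 + 3 = 47 days, then 62 − 44 = 18 to 118 − 16 = 102 days. A change from unhealed to healed between two such visits is known only to that interval, unless another source supplies a date. About 6 v 10 patients would contribute.

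**Step 6: the acute window.** Of the 57 permitted Month 3 days, days 91–118 (28 days, 49%) lie beyond the 90-day limit. A censoring rule must therefore say how a first grade 2+ found on those days is counted.

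**The case against.** The strongest reply is that little depends on this. The analyses are exploratory, section 8.3 stresses safety and tolerability as the main intention, and section 2.1.2 asks only to assess these times, so a descriptive report would satisfy it. Nor does section 8.3 say outright that a t-test will be applied to onset times. All of this is true and limits the weight of the point. It does not tell an analyst what value to give a patient without an event, and the t-test is the only method named for numerical outcomes.

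Four stronger readings are tempting, and the documents do not support them.

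- *Healing times would be misreported twofold.* Counted from the end of radiation, with assumed true medians of 14, 21 or 28 days, dating at the first healed visit rather than the interval midpoint does roughly double the median (1.5-fold at 42 days). Counted from the first grade 2+ assessment, the clock recommended here, the ratio is 1.33–1.79. Both calculations rest on assumed healing curves.
- *Healing can be dated only at scheduled visits.* Section 10.5 follows radiation- or product-related adverse events that are ongoing at the end of treatment until resolution or the end of follow-up. Section 5.7, on early discontinuation or termination, continues skin photographs until resolution. Neither sets a grading visit or a dating rule, but either may yield a resolution date.
- *The reported delay could reach 6.4–7.5 weeks.* That figure requires giving event-free patients a Month 3 onset date, and nothing in the documents suggests doing so.
- *Any first event up to the end of the Month 3 window counts.* Section 10.3 classes events from 90 days as late, so this would change the endpoint.

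**Conclusion.** The gap is real and worth closing, as a recommended wording change rather than a condition for the trial. At the plan's own rates about 65% of patients have no onset time. The two t-test readings considered reject in about 6–8% and 61–78% of simulated trials, against about 88% for log-rank. These figures assume proportional hazards, the three onset shapes and weekly grading over 7 weeks.

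A reader might infer that the trial loses power or that its main result is at risk. It does not: the primary comparison and the sample size of 39 stand, and log-rank gains only 1–2 points over chi-square on incidence. The benefit is a defined, reproducible onset analysis that uses all patients. For healing, the definition, grader and dating rule are missing. A censoring rule alone would not make that comparison a randomised one, because only affected patients enter it.

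**What to change.** 1. **Onset.** Replace the t-test for this endpoint with Kaplan-Meier and log-rank from the first radiation fraction, in the section 8.4 analysis set. Name the effect measure: for example a hazard ratio with 95% CI, or the difference in restricted mean time to a stated week, since the Dermaprazole median may not be reached. Censor event-free patients at their last skin assessment within the 90-day acute window. Show a first grade 2+ recorded at a Month 3 visit after day 90 only as a sensitivity analysis. Take the event date from one named grader, the same as for the primary rate, with the other as sensitivity. If that grader is the dermatologist, censor at the last graded photograph, since photography may stop early.
2. **Healing.** Define it by a stated CTCAE grade. Report Kaplan-Meier descriptively among affected patients only, from the first grade 2+ assessment, with unhealed patients censored at the last assessment. Treat the date as interval-censored unless adverse-event follow-up (sections 5.7 and 10.5) supplies a resolution date.
3. **Separate free improvement.** Compare SkinDex16 by ANCOVA or a mixed model with the collected baseline score as covariate. Relative to a follow-up-only comparison, the ANCOVA variance is 1 − ρ²: 0.91, 0.75 or 0.51 at assumed baseline correlations of 0.3, 0.5 or 0.7. ANCOVA on log values for the inflammatory markers is optional: the plan's use of relative changes is valid, and any power gain rests on assumed values.

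The cost is some SAP wording and slightly more analysis work. No new patients, visits or data are needed.

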8.2 Sample Size/Accrual Rate

Participants will continue to be enrolled and monitored for toxicity per the above criteria until 30 patients in arm 1 and 15 patients in arm 2 have completed the course of head and neck radiation as evaluable patients. Patients will be randomized by computer in a 2:1 fashion. Per our current database, the clinic is treating approximately 60 eligible patients per year. As such, accrual should take no longer than 12 months but will be allowed to extend to up to 24 months without closing the study.

Initial sample size for this pilot study was estimated as if this study was conducted as a phase II study. Sample size calculation was determined using significance/alpha (α) of 0.05, to at least detect a difference in incidence of 45% and power (β) of 80%. In general, rates of clinically bothersome grade II dermatitis in the literature appear to be approximately 65%. Based on our preclinical study with animal and human skin models, we expect 20% of the Dermaprazole arm to have CTCAE grade II or higher RD. Given these values, we calculated our final sample size to be approximately 39 and we aim to enroll 45 subjects.

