We will also evaluate any statistically significant differences in both the absolute numbers and relative changes of the lab values: CRP, TNFa, IL-1b, IL-6 at each of the 3 time points in which they are drawn for each arm.

All statistical tests will be two-sided. We will report comparative data in good faith and emphasize that the primary intention of this study is to understand the safety and tolerability profile of Dermaprazole.

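### Highest dermatitis grade is an ordered outcome, but the only categorical test named ignores order and gives no effect size; an order-respecting analysis is a cheap improvement to an exploratory endpoint

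*Combined protocol and SAP*

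**What the plan says.** Objective 2.2.2.1, in section 2.1.2, reads "To assess the highest grade of CTCAE version 5 radiation dermatitis during radiation treatment". Section 7 defines grades 1 to 5 by increasing severity, and section 8.3 describes the same scale: "Generally, adverse events in this system are graded from 1 to 5, with 1 corresponding to either mild or asymptomatic clinical manifestations of toxicity". The outcome is therefore ordered by the protocol's own definitions.

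The only sentence in section 8.3 that names tests for comparing the arms is "Chi square and t-test will be used to evaluate differences in categorical and numerical values between arms". No rank, trend, proportional-odds or exact method appears, and the sentence does not say which of its two tests applies to highest grade. The same section adds "All analyses outside of the primary endpoint will be considered exploratory in nature" and "All statistical tests will be two-sided".

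Section 8.2 plans 30 evaluable patients on Dermaprazole and 15 on Aquaphor. For Aquaphor it says that "rates of clinically bothersome grade II dermatitis in the literature appear to be approximately 65" per cent; for the cream, "we expect 20% of the Dermaprazole arm to have CTCAE grade II or higher RD". It gives no breakdown by individual grade and no power for highest grade.

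**The concern.** A grade is a category, so chi-square is the natural reading of section 8.3 for this objective. That test gives the same result if the grade labels are permuted, so it makes no use of the fact that grade 1 is better than grade 2 and grade 2 better than grade 3. A general move toward lower grades is one natural way for a preventive cream to work, and a test that uses the order is usually better at detecting it. Chi-square also yields only a p-value. It does not say which arm did better or by how much.

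The objective exists to recover what the binary grade 2 or higher outcome discards: the differences between grades 0 and 1, and between grades 2 and 3. In a pilot of 45 patients, an estimate with an interval is what would inform the next trial.

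**Working it through.** **Inputs from the documents.** Grade 2 or higher: 65% on Aquaphor, 20% on Dermaprazole. Patients: 15 and 30. Two-sided alpha 0.05, power 80% (section 8.2; sidedness from section 8.3).

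**The plan's own figure first.** With 2:1 allocation the pooled rate is (0.65 + 2 × 0.20)/3 = 0.35. Using the pooled-variance formula without continuity correction, the Aquaphor arm needs

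n = [1.960 × √(0.35 × 0.65 × 1.5) + 0.842 × √(0.65 × 0.35 + 0.20 × 0.80/2)]² / 0.45²
= [1.960 × 0.5842 + 0.842 × 0.5545]² / 0.2025
= 1.612² / 0.2025 ≈ 12.8, so 13.

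The total is 13 + 26 = 39, as section 8.2 states. This figure concerns the binary outcome only. With 15 and 30 patients, the exact power of the uncorrected binary chi-square at 65% v 20% is 86%.

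**Assumptions needed for highest grade.** The Aquaphor grade mix is assumed, always with 65% at grade 2 or higher. The Dermaprazole mix then follows from a common odds ratio. At the design effect this is (0.20/0.80)/(0.65/0.35) = 0.25/1.857 = 0.135. For example, Aquaphor 5/30/45/20% for grades 0/1/2/3 becomes 28.1/51.9/16.7/3.3% on Dermaprazole.

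**Sparse cells in that example.** The expected Aquaphor count is 15/45 of each column total:

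- Grade 0: (30 × 0.281 + 15 × 0.05)/3 = 3.1
- Grade 1: (30 × 0.519 + 15 × 0.30)/3 = 6.7
- Grade 2: (30 × 0.167 + 15 × 0.45)/3 = 3.9
- Grade 3: (30 × 0.033 + 15 × 0.20)/3 = 1.3

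Across all the mixes tried, 98 to 100% of simulated tables had at least one expected count below 5.

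**Power under a common odds ratio.** These are simulated trials of 15 v 30 (200,000 per scenario), comparing Pearson chi-square over all grades with the tie-corrected Wilcoxon rank-sum test, at the design effect:

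| Grades occurring | Chi-square | Wilcoxon | Gap (points) |
|---|---|---|---|
| 0 to 4 | 76–77% | 91% | 14 |
| 0 to 3 | 79–82% | 91–92% | 10–12 |
| 1 to 4 | 79% | 88% | 8–9 |
| 1 to 3 | 82% | 87–88% | 5–6 |

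The four-or-more-grade chi-square thus has less power here than the 86% of the simpler binary comparison. Over odds ratios of 1/5 to 1/2 the gap runs from about 4 points (grades 1 to 3 at 35/50/15%, odds ratio 1/2: 16.8% v 20.6%) to about 22 points (grades 0 to 4 at 5/30/40/20/5%, odds ratio 1/4: 42.0% v 64.0%).

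**Power when the shift is not common to all grades.** Aquaphor is 5/30/45/20%. Dermaprazole keeps 20% at grade 2 or higher and gains nothing at grade 0:

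| Dermaprazole, grades 0/1/2/3 | Chi-square | Wilcoxon |
|---|---|---|
| 5/75/15/5% | 77% | 78% |
| 5/75/10/10% | 80% | 71% |

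**Type I error.** With no difference between arms, chi-square rejects in about 4 to 5% of trials: 3.8% with grades 0 to 4, 4.7 to 4.9% with grades 1 to 3. Wilcoxon rejects in about 5%.

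**The case against.** **The plan may not intend this test.** Objective 2.2.2.1 states no between-arm hypothesis, and section 8.3 never assigns chi-square to it by name. This is right: a chi-square over all grades is inferred. The other reading, a t-test on the grade number, does use the order and would lose little power under a common shift. It treats the steps between grades as equal, however. On either reading no method designed for ordered grades is named.

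**The power loss is not a property of the plan.** A reader might take one plausible mix (5/30/45/20%) with a common odds ratio and Dermaprazole rates of 20%, 30% and 35%, obtain gaps of 11 to 18 points, and call that the cost of the plan. The documents do not support this. Proportional odds at the design effect implies 28% of Dermaprazole patients with no dermatitis at all, against 5% on Aquaphor. Section 3.1 says dermatitis occurs in most patients, and section 8.2 states the expected benefit only as fewer cases at grade 2 or higher. With nobody at grade 0 the gap is about 5 to 9 points, and some non-uniform shifts abolish or reverse it. This objection stands in full.

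**Sparse cells do little harm.** A reader might infer that low expected counts make the p-value invalid. In the simulations the test is slightly conservative at the 0.05 level, with no inflation. This also stands.

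**Little depends on it.** The analysis is exploratory, section 8.3 puts safety and tolerability first, and no decision rule uses this test. That limits the weight of the point but does not remove the gain from an interpretable estimate.

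**Conclusion.** The point holds as a cheap improvement to an exploratory analysis; it does not correct an error. From the documents alone, the outcome is ordered, the one test named for categories ignores that order, and that test supplies no direction or effect size.

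The size is conditional. With 30 and 15 patients and a common odds ratio across grades, the rank test gains about 5 to 14 points of power at the design effect and about 4 to 22 points at odds ratios of 1/5 to 1/2. If the benefit is concentrated at the step from grade 2 to grade 1, the gain can be nil or negative. The grade mixes and the form of the shift are assumptions. The figures use the large-sample Wilcoxon test, so they are a guide to the exact version.

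Nothing here touches the primary binary comparison or its sample size, which reproduces.

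**What to change.** Add to section 8.3 that highest grade (objective 2.2.2.1) will be compared between arms with a two-sided exact (permutation) Wilcoxon rank-sum test. Report the common odds ratio, or the probability of a lower peak grade on Dermaprazole with a stated rule for ties, with a 95% CI and beside the grade-by-arm table. The table lets a reader see whether the shift is uniform. Leave the binary grade 2 or higher comparison as planned.

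The cost is a sentence or two in the plan, with no new data and no change in sample size. It should be settled before outcome data are seen, so that the test is not chosen on the result. The downside is some loss of power relative to chi-square if the shift is not uniform across grades.

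### Section 8.3 names chi-square as the only between-arm test for categories; with 30:15 patients its p-values are unreliable for uncommon adverse events and small subgroups, within exploratory comparisons only

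*Combined protocol and SAP*

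**What the plan says.** Section 8.3 covers between-arm testing in one sentence: "Chi square and t-test will be used to evaluate differences in categorical and numerical values between arms". It adds that "All statistical tests will be two-sided" and that "Subgroup analyses for BMI, total dose, and comorbidity will be conducted", without cut-points or subgroup sizes. Everything outside the primary endpoint is labelled exploratory.

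For safety, the same section says "Toxicity will be reported as the frequency of each adverse event according to the CTCAE version 5.0", along with the grade of each event. That sentence is descriptive, but the chi-square sentence does not exempt adverse events from between-arm comparison.

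A significance level appears only in Section 8.2: "Sample size calculation was determined using significance/alpha (α) of 0.05". The same section fixes 30 evaluable patients in the Dermaprazole arm and 15 in the Aquaphor arm, randomised 2:1.

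**The concern.** Pearson's chi-square relies on a large-sample approximation that is poor when expected cell counts are small. Two features of this trial make that matter. The control arm has only 15 patients, so most individual adverse events will give small expected counts. And 2:1 allocation makes the statistic lopsided for rare events: one or two events in the smaller arm move it much more than the same number in the larger arm.

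Section 8.3 says the main purpose is to learn about safety and tolerability, and Section 10.3 says the cream has not been tested in humans. A table of adverse events with chi-square p-values could therefore mislead in two ways. Two chance events on Aquaphor could be reported as a significant advantage for Dermaprazole. A larger excess on Dermaprazole could be reported as not significant and taken as reassuring.

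**Working it through.** **Inputs.** From Section 8.2: arms of 30 and 15; alpha 0.05; 65% expected on Aquaphor and 20% on Dermaprazole ("we expect 20% of the Dermaprazole arm to have CTCAE grade II or higher RD"). From Section 8.3: chi-square, two-sided. Assumed, because the plan does not say: the uncorrected Pearson statistic, alpha 0.05 for exploratory tests, and subgroup sizes of 10:5, 12:6 and 15:7.

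**1. The plan's own figure, and which chi-square it implies.** With allocation ratio r=2, the pooled rate is (0.65 + 2×0.20)/3 = 0.35. The Aquaphor arm size without continuity correction is

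n = [1.960×√(1.5×0.35×0.65) + 0.842×√(0.65×0.35 + 0.20×0.80/2)]² / 0.45² = (1.145 + 0.467)² / 0.2025 = 12.8, rounded up to 13.

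This gives 13 + 26 = 39, the stated total. With a continuity correction the total is 48. The match supports reading the test as uncorrected, but that is an inference.

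**2. When expected counts are small.** The expected Aquaphor count is m×15/45 = m/3 for m events in all, so it is below 5 whenever m<15. At the planning rates the primary endpoint gives 0.20×30 + 0.65×15 = 15.75 events and an expected Aquaphor count of 5.25, just above that mark.

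**3. Thresholds at 30:15.** χ² = N(ad−bc)² / (n₁n₂m(N−m)), where a and c are the event counts, and b and d the non-event counts, in the two arms.

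- 0/30 v 2/15: χ² = 45×60²/(30×15×2×43) = 4.19, p=0.041. Fisher: C(15,2)/C(45,2) = 105/990 = 0.106. Yates: 0.20. Expected counts are 1.33 and 0.67.
- 6/30 v 0/15: χ² = 45×90²/(30×15×6×39) = 3.46, p=0.063.
- 7/30 v 0/15: χ² = 45×105²/(30×15×7×38) = 4.14, p=0.042; Fisher 0.077.
- Under Fisher the smallest one-sided splits reaching 0.05 are 0 v 3 (p=0.032) and 8 v 0 (p=0.038).

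**4. False-positive rates at 30:15.** All tables were enumerated under a common event rate, weighting each by its two binomial probabilities and splitting rejections by direction.

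| Common rate | Pearson, favours Dermaprazole | Pearson, favours Aquaphor | Fisher, favours Dermaprazole | Fisher, favours Aquaphor |
|---|---|---|---|---|
| 5% | 3.87% | 0.03% | 0.98% | 0.00% |
| 6% | 3.89% | 0.07% | 1.24% | 0.01% |
| 10% | 3.08% | 0.55% | 1.91% | 0.16% |
| 20% | 2.73% | 2.26% | 1.84% | 1.20% |
| 50% | 2.29% | 2.29% | 1.43% | 1.43% |
| 65% | 2.43% | 2.72% | 1.52% | 1.77% |

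Pearson's total size over all rates is at most 5.5%. At a 5% rate it is 3.9%, below nominal.

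**5. Assumed subgroups, Pearson (favours Dermaprazole / favours Aquaphor).**

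| Size | 20% rate | 50% rate | 65% rate |
|---|---|---|---|
| 10:5 | 4.6% / 0.2% | 2.4% / 2.4% | 1.3% / 3.7% |
| 12:6 | 5.0% / 0.5% | 3.3% / 3.3% | 2.3% / 4.0% |
| 15:7 | 4.4% / 1.3% | 3.4% / 3.4% | 3.0% / 3.7% |

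Maximum total size is 6.7% (12:6) and 6.8% (15:7), both at a 50% rate, where the two directions are equal.

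**6. What an interval shows.** For 0/30, the exact upper 95% limit is 1 − 0.025^(1/30) = 11.6%.

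**The case against.** The strongest reply is that no safety decision depends on this test. Section 8.3 defines safe by fixed rates: under 50% for grade 1, under 10% for grade 2 or higher, none at grade 3 or higher. Section 8.1 adds a 50% moderate-toxicity rule and stops the trial for two treatment-related grade 3 serious events, or one at grade 4-5, on Dermaprazole. Section 10.5 sends any run of three or more of the same event to independent review. This stands, and it limits the point to exploratory comparisons.

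It also rules out two inferences a reader might draw. One is that harm from Dermaprazole goes unnoticed until seven events against none. Seven is only the Pearson threshold: 3 grade 2 events in 30 is 10% and already fails the under-10% criterion. The other is that the plan would declare the cream safe because a test was not significant. Its criteria do not work that way; the risk lies in how exploratory p-values are read.

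Three further objections hold in part.

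- *The statistic and alpha are assumed.* True. If Yates's correction was meant, 0/30 v 2/15 gives p=0.20. The text therefore allows opposite readings of one table, which is itself a reason to specify the method.
- *Subgroups are not tilted in general.* True. A reader might infer a general tilt towards Dermaprazole, but it needs sparse outcomes, disappears at 50% and reverses at 65%. The subgroup sizes are illustrations.
- *Fisher does not cure the asymmetry.* True. It comes from 2:1 allocation with few events, and Fisher needs a larger Dermaprazole excess before it flags one.

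**Conclusion.** The point holds as a limited one about method. For sparse tables the single test named in Section 8.3 can give a misleading p-value, and a better-suited method is readily available. The clearest case is two Aquaphor events against none, where Pearson and Fisher fall on opposite sides of 0.05. For rare events at 30:15 the fault is in the direction of the false positives. General inflation of the type I error, which a reader might also infer, is not supported at that size. Modest inflation appears only in some small subgroups, and there it is greatest where no tilt exists.

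The conclusion assumes the uncorrected statistic, alpha 0.05 for exploratory tests, full arms of 30 and 15, and subgroup sizes that the plan does not give. The primary comparison is not in question: chi-square at 30:15 is adequate there.

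**What to change.** Add to Section 8.3:

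> Where any expected cell count is below 5, categorical comparisons other than the primary endpoint use Fisher's exact test; adverse-event rates are reported per arm with exact (Clopper-Pearson) 95% CIs, and non-significance is not interpreted as evidence of safety.

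This changes neither sample size, conduct nor the primary analysis. The cost is some power in exploratory comparisons, including power to flag an excess on Dermaprazole: with no Aquaphor events, 8 are needed instead of 7. At a 10% event rate the Fisher split is still 1.91% to 0.16%, so the change of test alone is not enough. The exact intervals should carry the safety interpretation: even with no events among 30 patients, the upper limit of 11.6% lies above the plan's own 10% criterion for grade 2 or higher toxicity.
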